Little is known about the essential components of MBC. Models of MBC vary in a number of ways, including the frequency and content of assessment, the format and target of feedback, etc. Efforts to draw conclusions about these components have been hampered by differences between studies, and there is a need for studies to directly compare different forms of MBC²⁰. One key issue that has cascading effects across the entire MBC process is what assessment data to gather. Current approaches can be grouped into *unidimensional* approaches that track symptoms²⁶⁻³⁶ and multidimensional approaches that also track therapy processes such as therapeutic alliance^{37,38}. Because multidimensional MBC focuses on both treatment progress and processes, it leads to feedback that is more actionable than unidimensional approaches, which only provide feedback on symptoms. Actionable feedback is key to MBC success^{19,39-41}; multidimensional MBC may therefore be more effective. It also recognizes patient and caregiver preference for measures that assess positive aspects of treatment progress⁴²⁻⁴⁶. However, multidimensional MBC may have higher burden for clients and clinicians than unidimensional MBC, which could have implications for fidelity and sustainability.

Systematic reviews and meta-analyses of MBC have not discriminated between these approaches^{13-20,47}. However, individual randomized controlled trials (RCTs) have supported both approaches. Multidimensional MBC has been shown to be more effective than controls, with small-to-medium effects in adults⁴⁸⁻⁶⁰ and small effects in youth^{37,38}. Unidimensional approaches have small effects in adult samples^{26,27,30-36}, but the only youth study found no effect of feedback. Further, MBC effectiveness may be moderated by whether a client is on-track (OT) or not-on-track (NOT) for improved outcomes, with MBC found to be most beneficial for clients flagged as NOT^{51,59,60}. The only direct comparisons for multidimensional and unidimensional MBC have occurred within the NOT group. Three studies have examined the effects of adding a single administration of a multidimensional MBC battery after a unidimensional system flags an adult client as NOT^{51,59,60}, finding improved outcomes for the group that received the multidimensional feedback ($d = .31^{51}$).

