Youth and their caregivers will be included in Aims 2 and 3 in three ways. First, the four study clinics will be using the measurement-based care system with all clients receiving in outpatient and intensive outpatient mental health services (up to 2000 youth falling in the target age range) and have agreed to incorporate the study randomization scheme as a quality improvement effort. PI [name] has successfully used this approach in two previous randomized controlled trials of MBC^{46,47}. Second, in the session where the youth and caregivers complete the MBC measures through the Mirah platform, they will be recruited via the Mirah Platform to complete additional measures using the same procedures described for the Study 1 pilot trial. Recruitment will take the form of presenting a recruitment screen, followed by the consent form if they indicate they are interested in learning more about the study at the end of their measures; families will also be notified that this will be happening via a flyer that the clinic will be using to tell them about the Mirah system. These flyers are tailored for each office, but we have uploaded one as an example (Mirah PACE flyer- Nashville). We have also uploaded a copy of the recruitment screen (Recruitment Information for Research Subsample). The clinics may use Mirah at the clinic intake session, before the decision has been made which services the youth will receive. If a family consents to be in the research sample and then the youth does not go on to be assigned to one on the services using Mirah, they will be contacted and informed that they will no longer be eligible to take part in the study. Up to 400 youth and their caregivers will be enrolled in these additional research activities. Finally, for the final phase of the mixed-method study of implementation factors, a subset of up to 12 families who agreed to take part in the research study, stratified by their level of adherence to the MBC system, will be recruited with the assistance of their clinicians, who will provide them with a flyer describing the study (uploaded as PACE Family Triad Interview Recruitment Flyer) and asked if they would be interested in being contacted by research staff to hear about an opportunity to participate in qualitative interviews to better understand their experiences using the system. Families will be paid up to \$60 in gift cards (\$30 per informant) for participating in those interviews.

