The primary study endpoints are the youth- and caregiver-reported Symptoms and Functioning Severity Scale and the youth- and caregiver-reported Ohio Problems and Functioning Scale (Research Subsample Only)

10) Procedures Involved*

Below, we present a general overview of the study methods as outlined in the grant proposal. Please note that this R34 development grant is designed to generate procedures iteratively over the course of the study, so materials and procedures will be updated and submitted as they are developed through the procedures outlined below.

METHODS FOR AIM 1: PRELIMINARY DEVELOPMENT ACTIVITIES

The goal of Aim 1 is to conduct development activities to ensure fit between agency workflow and the MBC system, implementation support tools, and research procedures. In **Development Phase 1 (Aim 1a)**, qualitative data collection will refine research measures and protocols, and assess potential implementation barriers and facilitators. Three qualitative components will be conducted with semi-structured protocols. First, either at the initial site visit or via phone or video conferencing shortly thereafter, individual or group interviews will be held with agency leaders (1-3 per clinic, for up to 15 interview participants) to help develop procedures for the pre-pilot study and discuss organizational-level factors that may influence MBC implementation. Second, individual or group interviews will also be held at the initial site visit or via phone or video conferencing shortly thereafter with up to 10 eligible clinicians combined from all five clinics. The interviews will gather information about clinical decision-making, typical clinic workflow, and any existing strategies for tracking treatment progress. Participants in individual and group interviews will respond to open-ended questions and be asked to react to sample MBC materials, study measures, and study procedures, and will be paid \$20 per hour for their time. Interviews will last 30 to 90 minutes, depending on participant availability and preferences. The interviews will be recorded and transcribed for coding, with results used to modify the project materials. The interview questions have been submitted under study documents.

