Procedures for effectiveness trial. After Aim 1 is complete, program-wide implementation of MBC will begin. The initial training will consist of a series of workshop style trainings conducted during regular agency staff meetings and ongoing consultation will be provided to agency staff thereafter. The training approach is a data-driven one, where questionnaires are used throughout the training and consultation to tailor implementation to that specific context. These questionnaires will be considered part of the implementation activities and will be administered to all staff members participating in the trainings. Clinicians who consent to be in the research study will be giving permission for these implementation data to be linked to the research data they provide for their clients; responses from other HCA staff will be de-identified and used to characterize the implementation under Aim 3. Prior to extracting these data for research purposes, we will submit a variable list to the IRB for approval. When the initial training is complete, the trial will begin program-wide at the participating HCA clinics. As the clinics add clients ages 11-17 to the Mirah system, the system will automatically randomize them to either unidimensional or multidimensional MBC on a 1:1 ratio. All clients and their caregivers will complete MBC measures as part of routine services, and the researchers will receive limited identifier datasets containing MBC data and Mirah metadata for all participants, an identifiable

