dataset for individuals who consent to take part in the research subsample. We have uploaded a variable list of the variables we will be requesting from Mirah. After the first time a youth and their caregiver complete the MBC measures, the Mirah system will proceed to screens with recruitment and consent information for participation in the Research Subsample. Youth and caregivers will be asked to assent/consent to complete additional research measures. Each time they complete Mirah measures for routine sessions, youth and caregivers will be administered one additional mechanism item; this item will be included in up to 12 sessions after they enroll in the study. In addition, they will complete a longer set of research measures will including the Ohio Scales and additional mechanism measures; these will be administered at study enrollment, 6 weeks later, and 12 weeks after study enrollment. These longer sets of research measures will be administered via the REDCap system, with links e-mailed directly to the family by research staff. Additional Research Subsample Measures have been uploaded under Study Documents. Families who consent to be a part of this Research Subsample will be paid up to \$30 for completing these measures (the project will e-mail them a \$10 gift card per major assessment completed either directly through e-mail or by using Qualtrics and Tango Card). Clinicians treating clients in the Research Subsample will also be asked to complete additional measures for those clients and will be paid \$36 for completing those measures. The Mirah system does not have a way to only recruit clients whose clinicians have consented to be in the research study or to tailor the measure schedule for those clients. Therefore, if a client agrees to be in the study and their clinician has not, the study will contact the clinician, let them know that they will be receiving links to research measures, and see whether they would like to consent to be in the study at that point. If they do not, then they will be instructed to disregard the requests for them to complete measures. These measures are also included in the Research Subsample Measures upload under Study Documents.

METHODS FOR AIM 3. MIXED-METHODS ANALYSIS OF IMPLEMENTATION FACTORS

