Clients and Caregivers in the Research Subsample. At least 420 clients and caregivers will complete additional research measures via the Mirah system during the Aim 1c pre-pilot and the Aim 2 trial. Consent procedures will differ slightly for the two phases of the study. For the pre-pilot, caregivers will view a consent form and youth an assent form the first time they complete these measures in the Mirah system. If they have questions before participating, they will have the option to provide a phone number and ask for a call from study staff before deciding. For the Aim 2 Research Subsample, which involves a much larger sample of youth being recruited when they start treatment, youth and caregivers will view recruitment information when they complete their clinic intake questionnaires via Mirah. If they click that they are interested in the study, they will proceed to a screen with the consent/assent document. After reading the document, they will indicate yes, no, or "I have questions." If they have questions, they will next proceed to a Frequently Asked Questions (Research Subsample Frequently Asked Questions Page, uploaded in consent materials) page to see if their question is there. If not, they will be provided with the project phone number to call to ask questions. If they indicate at the intake that they have questions and do not consent, the study recruitment and consent/assent information will be presented one more time prior to their completion of the Mirah measures for their first session. If they do not agree to be in the study at that point, they will no longer be eligible to be part of the research subsample. Because youth and caregivers receive different links to complete their Mirah questionnaires, they will be asked to assent and consent separately, and it is possible that youth may consent prior to their caregivers consenting. However, neither youth nor caregivers will complete research measures unless both have consented/assented. We are requesting a waiver of signed consent for both the pre-pilot and research subsample subsample participants. For the pre-pilot obtaining written consent would increase the study risk by providing identifying information to the study team. For the research subsample, the research

team will obtain identifying information from participants in order to give them gift cards, but the study is online, so it is not feasible to get signed consent and the study is minimal risk.

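### The Ohio endpoints and research-only mechanism measures are compared in an opt-in group formed after randomisation, and the Aim 2c model names no adjustment for who opts in (minor; cheap improvement)

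*Combined protocol and SAP*

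**What the plan says.** **Order of events in Aim 2.** Section 10 (Procedures for effectiveness trial) says that as clinics add clients aged 11-17 to Mirah, "the system will automatically randomize them to either unidimensional or multidimensional MBC on a 1:1 ratio". The invitation comes later: "After the first time a youth and their caregiver complete the MBC measures, the Mirah system will proceed to screens with recruitment". Section 7 agrees: "in the session where the youth and caregivers complete the MBC measures through the Mirah platform, they will be recruited via the Mirah Platform". Section 30 places the invitation at intake: "youth and caregivers will view recruitment information when they complete their clinic intake questionnaires via Mirah". It allows one repeat before the first session's measures for families who had questions, and requires both youth and caregiver to agree.

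**What is measured only after opt-in.** Section 9 lists among the primary endpoints the "youth- and caregiver-reported Ohio Problems and Functioning Scale (Research Subsample Only". Section 10 says of the Ohio Scales and the longer mechanism measures that "these will be administered at study enrollment, 6 weeks later, and 12 weeks after study enrollment". At routine sessions, enrolled "youth and caregivers will be administered one additional mechanism item".

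**Analysis (section 12).** Aim 2c compares SFSS trajectories, Ohio scores and mechanisms by condition, nested within clinician and controlling for clinic. The fallback is an analysis of variance for time by treatment. As a first step, mechanism scores are averaged or summed across sessions. Aim 2b examines factors linked to condition, client or clinician, and compares the subsample with the full sample on health-record data. Section 8 also schedules an enrolment and attrition analysis by arm. The stated use of the Aim 2b results is the design of the R01. Further covariates are mentioned only under Aim 2d and are not listed.

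**The concern.** Randomisation balances all clients allocated. It does not by itself balance the roughly 400 of 900 who later agree to extra measures. If the arm influences who agrees, the enrolled groups can differ in prognosis, and part of any difference in Ohio or mechanism scores would then reflect who enrolled.

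The documents give one reason why the arm might matter. Section 4 expects that "multidimensional MBC may have higher burden for clients and clinicians than unidimensional MBC", and in Aim 2 the invitation follows the first measure set. They do not say whether that first set differs by arm, or whether families can tell which arm they are in.

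The SFSS comparison is outside this point. SFSS comes from routine MBC data on all randomised clients, so this opt-in does not affect it, though it still depends on measure completion.

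**Working it through.** **1. Sequence.** The section 10 order is allocation, first MBC measures, invitation, then research measures. Other wording is looser. Section 7 describes pre-pilot families being randomised after they agree and says Aim 2 recruits by the same procedures. Section 10 (Aim 1c) calls the pre-pilot procedures identical to Aim 2. The section 10 text on the effectiveness trial is the specific Aim 2 statement, so I take it to govern.

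**2. Inputs.** The plan gives no figure for opt-in effects. From section 12: 900 randomised, 400 enrolled, 8% of variance at clinician level, p = .05 (taken as two-sided). Enrolment is 400/900 = 44.4%. Everything else is assumed:
- a standard-normal prognostic factor that drives enrolment through a logistic model, with an odds ratio (OR) per SD in each arm;
- enrolment of 44.4% in both arms, or 42.4% v 46.4% either way;
- a correlation r between factor and outcome of .1 to .2 for later Ohio change, and .2 to .5 for a mechanism level.

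**3. Formulae.** D is the difference between arms in the mean factor among enrolled clients. Spurious d = r x D. SE = 2 x sqrt(.92)/sqrt(400) = .096. Type I error = P(Z < -1.96 - d/SE) + P(Z > 1.96 - d/SE).

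Example, OR 1.65 v 1.0 with equal enrolment: D = .263 - 0 = .263. At r = .2, d = .053 and d/SE = .55, so type I error = .006 + .079 = 8.5%.

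| OR per SD, arm v arm | D at 44.4% in both (range) | Ohio change: d; type I | Mechanism level: d; type I |
|---|---|---|---|
| 1.22 v 1.0 | .109 (.106-.113) | .011-.023; 5.1-5.6% | .021-.057; 5.6-9.1% |
| 1.65 v 1.22 | .153 (.140-.167) | .014-.033; 5.2-6.4% | .028-.084; 6.0-14.0% |
| 1.65 v 1.0 | .263 (.253-.272) | .025-.055; 5.8-8.8% | .051-.136; 8.3-29.5% |
| 1.65 v 1.65 | 0 (up to .019) | at most .004; 5.0% | at most .010; 5.1% |

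The last row is the case where selection is the same in both arms and only the rates differ, by 4 points.

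**4. Sensitivity to the enrolment share (1.65 v 1.0, equal arms).** If 6/7 of the 900 are aged 11-16, the share is 400/771 = 52%; change gives .023-.045 and level at r = .5 gives .114. If flow reached 2000, the share is 20%; change gives .039-.077 and level at r = .5 gives .193.

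**5. Sensitivity to the SE.** The plan's power of .62 at d = .25 implies SE = .25/(1.96 + .305) = .110. The largest type I errors then fall from 29.5% to 23% and from 8.8% to 7.9%. I could not reproduce .62 from the printed inputs alone (.664 with no between-clinician variance in the effect, .533 with .08). An unstated variance of .02 gives .627, so I do not call it wrong, and this point does not depend on it.

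**6. What Aim 2b could detect (450 per arm).** A comparison of enrolment rates has power .33 for a 5-point gap and .86 for a 10-point gap. With equal rates it has no power beyond its 5% false-positive rate to see that different families enrol in each arm. An arm-by-factor interaction, with the factor measured directly, has z = .199/.135 = 1.47 (power 31%) for 1.22 v 1.0, .302/.141 = 2.14 (57%) for 1.65 v 1.22, and .501/.140 = 3.57 (95%) for 1.65 v 1.0.

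**The case against.** The strongest reply is that harm requires opt-in to depend on arm, and nothing shows that it does. The invitation is automated, which limits recruiter influence, and at intake at most one questionnaire set precedes it. This stands, and it is why the point is conditional.

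Second, the one documented route is burden, which would most naturally change how many enrol. With the same selection in both arms, a 4-point gap gives at most .01 in the table. Larger gaps can do more. If the whole propensity to enrol correlates .1 to .5 with outcome, a normal selection model gives .017 to .085 for 10 points, but the planned by-arm check would probably see a gap of that size. The larger figures in the table need selection slopes that differ by arm, and no text supports calling that the main route.

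Third, Aim 2b already looks at demographic and clinical factors as well as rates, and feeding the results into the R01 suits a pilot. That is fair, but no arm-by-factor test is stated and nothing carries the result into Aim 2c.

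Fourth, treating mechanism scores as levels is a reading. Section 12 calls aggregation a first step, and the longer measures are repeated, so change models are possible for them.

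A reader might infer that the Ohio comparison is biased or that randomisation has failed. The documents support neither. They leave a route open and name no adjustment for it.

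**Conclusion.** The point holds in a limited form. The Ohio endpoints and research-only mechanism measures are compared in a group formed after allocation, and Aim 2c does not address opt-in.

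Size and direction are unknown. At 44.4% enrolment and under assumed arm-specific selection, the spurious effect is about d = .01 to .05 for Ohio as change, small against the subsample's target of d = .30. For mechanism scores compared as levels it is about .02 to .14, the upper end needing an OR of 1.65 in one arm against none in the other and r = .5. Change is the likelier reading for Ohio, given the repeated measurements and the fallback test, but section 12 does not spell it out. Change analysis removes differences already present at enrolment, not selection related to later change.

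If the first set is identical across arms and the arm is not visible, what remains is mainly generalisability. Severity is minor; this is a cheap improvement.

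**What to change.** **In Aim 2c**
- Analyse Ohio as change from the enrolment score, with the first-completed SFSS and its interaction with time as covariates. A main effect of SFSS alone adjusts the level, not the change.
- Include that SFSS in the mechanism models, plus the enrolment score where one exists. This assumes the SFSS is in the first MBC set, which the sponsor should confirm. Enrolment scores come through e-mailed links, so they may follow some exposure to MBC.
- Add one sensitivity analysis weighted by the inverse of arm-specific enrolment probability, estimated from that SFSS and health-record factors among randomised clients aged 11-16 who completed the first set. Run it whatever Aim 2b shows, since the interaction test has only about 30% power for modest selection.

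**In Aim 2b**, add arm-by-factor interactions for enrolment.

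**In the text**, state what families see before the invitation, and reconcile the pre-pilot and Aim 2 wording on when randomisation occurs.

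**Cost.** No new data collection, if the SFSS is in the first set. In a simulation at 1.65 v 1.0, the weighted variance rose by up to 8% in one arm. Correction is partial because only measured selection is removed: if the SFSS correlates .5 with the factor driving enrolment, a change bias of .05 falls to .04 and a level bias of .135 to .10.

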In **Development Phase 2 (Aim 1b)**, we will develop algorithms to identify NOT and OT trajectories for the SFSS to generate alerts that will be embedded into the MBC feedback reports, support moderator analyses of intervention condition by OT/NOT effects, and set the stage for the randomization scheme for the R01 SMART. Analyses will utilize existing limited identifier datasets from 2 previous RCTs^{46,47}, including data from 597 youth treated by 165 clinicians using multidimensional MBC at 30 sites. During this phase, Mirah staff will also embed study measures into the system, update feedback reports with the alerts, and build a system to automate study randomization.

In **Development Phase 3 (Aim 1c)**, five clinicians will pilot the MBC system with up to 4 clients each; clinicians will select clients from their own caseloads based on the clinician's decision that it would be appropriate to begin using MBC with the client. Before beginning to treat their clients in the pre-pilot, clinicians will complete a packet of some or all of the baseline

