Quantitative Analyses. Aims 1b and 2 will involve using multilevel modeling (MLM) approaches¹²⁵, to account for nesting of repeated measures within clients and clinicians. In all Aim 2 models, we will treat site as a fixed effect, due to the limited number of clinics (n=3). For **Aim 1b**, on-track (OT) and not-on-track (NOT) algorithms will developed using an extant dataset^{46,47} (N = 597). Analyses will progress in two stages, following established procedures previously applied to the Outcomes Questionnaire system¹¹⁸⁻¹²⁰, the most widely-tested MBC system¹⁹. The first stage of the analysis involves generating expected change trajectories for SFSS scores over time. MLM will be used to estimate these individual change trajectories with weekly scores nested within participants, who are in turn nested within therapists. Models will be tested using the Hierarchical Linear Modeling (HLM) software package¹²⁶ and restricted maximum likelihood (RML) estimation. Prior to hypothesis testing, we will examine SFSS distributions and apply transformations (e.g., square root, logarithmic) for the weeks in treatment variable as necessary¹¹⁸.

The second stage of the analysis involves: (1) developing a system to identify cases at risk of showing treatment deterioration (NOT), and (2) testing its predictive accuracy. Identification of NOT cases is based on the expected change trajectories (intercepts, slopes, and random effects) estimated in Stage 1. Following Cannon et al¹¹⁸, we will split the data into two random samples, a reference sample and a validation sample. As a first step, the base rate of treatment

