deterioration—a significant worsening of symptoms over the course of treatment—will be identified in the reference sample. Consistent with previous studies¹¹⁸⁻¹²⁰, identification of the base rate will be based on a combination of the reliable change index¹²⁷ (RCI) and clinical cutoff scores. Established SFSS values for the RCI and the clinical cutoff score¹²⁸ will be used to identify cases with clinical deterioration, operationalized as an SFSS increase over treatment exceeding the RCI and a case ending treatment in the clinically significant range of functioning. The deterioration base rate from the reference sample will serve as a basis for deriving prediction intervals around the expected mean change trajectory in the validation sample. Cases identified as exceeding the prediction interval at any point during treatment will comprise the NOT group. Cases within the interval form the OT group.

The validation sample will then be used to check the validity of the warning system in predicting true treatment deterioration. Analyses will examine whether classifying a client as NOT accurately predicts whether they end treatment classified as deteriorated. Sensitivity and specificity will be calculated and the algorithms will be adjusted as needed until adequate levels are reached, using Cannon et al.’s¹¹⁸ specificity values of .55 and specificity values of .75 as guides. We will then test the predictive validity of the finalized OT/NOT algorithm (**Aim 2a**) using the full RCT sample (N = 900). To prepare for the SMART R01, we will also conduct simulations, varying estimates entering the expected change trajectories to investigate transition points in the OT/NOT intervals to assess optimal timing of when to conduct the second randomization.

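### If the OT/NOT algorithm is adjusted after it is scored in the validation sample, the Aim 1b accuracy is apparent rather than validated, and the adequacy check can be passed by chance

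*Combined protocol and SAP*

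**What the plan says.** Section 10 (Development Phase 2, Aim 1b) describes the development data as "including data from 597 youth treated by 165 clinicians using multidimensional MBC at 30 sites". One stated purpose of the algorithm is to "generate alerts that will be embedded into the MBC feedback reports"; it also supports the moderator analyses.

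Section 12 (Quantitative Analyses) gives the steps:

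- Stage 1 fits SFSS change trajectories by multilevel model. Stage 2 builds on them: "Identification of NOT cases is based on the expected change trajectories (intercepts, slopes, and random effects) estimated in Stage 1".
- For Stage 2, "we will split the data into two random samples, a reference sample and a validation sample". The ratio is not given, and no third sample is mentioned.
- The reference sample supplies the rate of deterioration. The step that uses this rate is worded as "deriving prediction intervals around the expected mean change trajectory in the validation sample".
- The validation sample is used to see whether NOT status predicts ending treatment deteriorated. Sensitivity and specificity are calculated, and "the algorithms will be adjusted as needed until adequate levels are reached". Values of .55 and .75 from a cited study serve as guides. Both are labelled specificity; I read .55 as the sensitivity guide.
- The finalized algorithm is then tested in the full RCT sample, N = 900 (Aim 2a).

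The section describes no cap on adjustments, no cross-validation, no optimism correction and no fresh hold-out before launch.

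**The concern.** A validation sample gives an honest accuracy estimate only while it plays no part in choosing the rule. Here a disappointing result in that sample triggers a change to the rule, and the only historical data available for re-scoring have already been used. The split is there to provide independence, and the adjustment loop gives it up.

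Two things are at stake. The first is the Aim 1b accuracy estimate, which would be too favourable. The second is the decision that the algorithm is good enough to launch, because a weak rule gets several chances to clear the guides. That decision matters downstream: the algorithm drives the alerts clinicians see, defines the Aim 2d moderator, enters an Aim 2c mechanism composite and informs the planned SMART.

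**Working it through.** The protocol states no achieved sensitivity or specificity, only guide values, so there is no figure to reproduce. The check asks what the adjust-until-adequate rule does to the values that will be calculated.

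**Inputs from the protocol**

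- Development data: 597 youth.
- Guides: .55 (read as sensitivity) and .75 (specificity).
- Rule: adjust until adequate.

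**Assumptions, because the protocol does not give them**

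- 50:50 split: 597/2, about 298 youth in the validation sample.
- Deterioration base rate of 10% or 15%: 298 × .10 ≈ 30 deteriorated and 268 not; 298 × .15 ≈ 45 and 253.
- Variants of the rule have latent scores correlated .8 and equal true accuracy.
- Up to 5 or 10 variants are tried, stopping at the first that meets the guides.

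**Step 1. Precision of one look.** SE = √(p(1−p)/d), with p = .55.

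- d = 30: √(.55 × .45/30) = .091; exact 95% interval about .34 to .72.
- d = 45: √(.55 × .45/45) = .074; exact 95% interval about .40 to .70.

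Sensitivity rests on few youth, so a guide value is easily missed or met by chance.

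**Step 2. One locked rule, true sensitivity .45 and specificity .75.** The chance of meeting both guides is the product of two binomial tails.

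- 10% base rate: at least 17 of 30 (.55 × 30 = 16.5) has probability .136; at least 201 of 268 (.75 × 268 = 201) has probability .533. Product: .136 × .533 = .07.
- 15% base rate: at least 25 of 45 (24.75) has probability .102; at least 190 of 253 (189.75) has probability .519. Product: .102 × .519 = .05.

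A rule that falls short on sensitivity therefore passes about 5-7% of the time when scored once.

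**Step 3. The same rule, with adjustment on the same sample.** Simulation under the assumptions above, counting runs in which any variant meets both guides:

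| Variants tried | Chance of meeting .55/.75 |
|---|---|
| 1 (locked) | about 5-7% |
| 5 to 10 | about 16-31% |

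The low end is 5 variants at a 15% base rate; the high end is 10 variants at 10%.

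**Step 4. Optimism when the rule is adequate.** With true sensitivity .60, stopping at the first adequate variant gives a mean excess of apparent over true sensitivity of about .01 to .03. At a 10% base rate it is .023 (5 variants) or .027 (10) if adequacy is judged on sensitivity alone, and .015 or .020 if both guides must be met. It is somewhat smaller at 15%.

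**Step 5. How likely is any adjustment?** Suppose the guides are treated as hard thresholds and a rule has true accuracy .60/.75. At a 10% base rate its first version meets the sensitivity guide with probability .715 and both guides with probability .715 × .533 = .38. Adjustment could therefore well be triggered even for an adequate rule, though the protocol calls these values guides and may apply them loosely.

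**The case against.** Several points on the other side stand.

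- **Adjustment is conditional.** If the first version is judged adequate, there is no re-tuning bias.
- **Where the intervals are set is ambiguous.** A reader might infer from "prediction intervals around the expected mean change trajectory in the validation sample" that the intervals are trained on the test data as a matter of course. The phrase can equally mean that they are applied there. The trajectories come from Stage 1, the base rate comes from the reference sample, and the text describes no use of validation-sample outcomes to set the intervals. The point therefore rests on the re-tuning step, which follows scoring in that sample on either reading.
- **The size depends on the stopping rule.** Picking the best of 5-10 variants would inflate sensitivity by .06-.08 at a 10% base rate. The protocol describes stopping when adequate, not picking the best, so that larger figure does not apply.
- **The historical data are not free of feedback.** Those youth were treated under multidimensional MBC. A reader might infer that tuning spends the one accuracy estimate untouched by feedback; the most the documents support is that this algorithm's own alerts were not yet acting.
- **Aim 2a is a real test** of the finalized rule in N = 900 new clients. At a 10% base rate (90 deteriorated), the 95% interval around a sensitivity of .55 would be about .45 to .66.

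Aim 2a does not remove the point. It comes after the launch decision and with alerts live. Section 4 says MBC alerts prompt clinicians to change strategy, so a correct alert that averts deterioration would count as a false positive.

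**Conclusion.** The point holds, with limits. If any adjustment is made after scoring in the validation sample, the Aim 1b accuracy is apparent, and the adequacy criterion is easier to meet by chance than a single look would make it. For an adequate rule (true sensitivity .60) the inflation is small, about .01-.03. The larger effect is on the launch decision: a rule with true sensitivity .45 and specificity .75 passes in about 16-31% of runs with 5-10 variants, against about 5-7% when locked.

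These sizes rest on the assumed split, base rate, correlation and number of variants, and on reading .55 as the sensitivity guide. The direction does not depend on the split or base rate.

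A reader might infer that the randomised comparison, or OT/NOT status as a moderator, is biased as a result. The documents do not support that: optimism in an accuracy estimate does not change the allocation or the outcome scores. What can follow is that a rule less accurate than believed is put into use.

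**What to change.** In section 12, Aim 1b:

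1. Fit the trajectories, base rate, intervals and all threshold tuning in the reference sample only, using cross-validation with each clinician's clients kept together. Split the two samples by clinician as well.
2. Lock the rule, score it once in the validation sample, and report sensitivity and specificity with 95% intervals.
3. Correct the label so that .55 and .75 each have a clear meaning.
4. If the rule is adjusted after that single scoring, label the Aim 1b figures as apparent, report a bootstrap optimism-corrected estimate that repeats the whole tuning process, and rest the accuracy claim on Aim 2a, noting that alerts were live.

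Step 4 may be the one that applies. This is version 20, dated 05/20/24; Aim 1b precedes the trial, and section 10 already speaks of clinicians joining in the past tense. The algorithm may therefore already exist.

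The cost is modest extra analysis (the grouped cross-validation or the bootstrap) and slightly less favourable reported accuracy. No new participants are needed. Precision in the validation sample stays limited, which the intervals will show.
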